9.2. Plasma concentrations and pharmacokinetic parameters

9.2.1. Plasma parameters

- [REDACTED]
- [REDACTED]
- [REDACTED]
- [REDACTED]
- [REDACTED]

Relevant plasma pharmacokinetic (PK) parameters will be calculated for RO7017773, and Itraconazole and its metabolite (hydroxy-itraconazole) by standard non-compartmental methods for the subjects with sufficient plasma concentration data. The rules defined in the previous section (9.1) will be used.

The different areas under the concentration-time curve (AUC) will be calculated using the linear-log trapezoidal method.

Parameters (unit)	Definition
C_{\max} (unit)	Maximum observed plasma concentration
T_{\max} (h)	Time to reach maximum observed plasma concentration
C_{last} (unit)	Last observed plasma concentration
T_{last} (h)	Time to reach last observed plasma concentration
AUC_{0-24} (unit.h)	Area under the plasma concentration-time curve from time zero to 24 hours (only for Itraconazole)
AUC_{0-72} (unit.h)	Area under the plasma concentration-time curve from time zero to 24 hours (only for RO7017773)
$AUC_{0-\text{last}}$ (unit.h)	Area under the plasma concentration-time curve from time zero to the last measurable plasma concentration
$AUC_{0-\infty}$ (unit.h)	Area under the plasma concentration-time curve from time zero to infinity, calculated as follows: $AUC_{0-\infty} = AUC_{0-\text{last}} + C_{\text{last}}/\lambda_z,$ where C_{last} is the last quantifiable concentration
$T_{1/2}$ (h)	Apparent terminal elimination half-life, calculated as follows: $T_{1/2} = \ln(2)/\lambda_z$
λ_z (h ⁻¹)	Apparent terminal elimination rate constant

Parameters (unit)	Definition
CL/F (L/h)	Apparent total body clearance, calculated as follows: $CL/F = \text{Dose} / AUC_{0-\infty}$

Parameters (unit)	Definition
-------------------	------------

Parameters (unit)	Definition
$R_{C_{max}}$ (no unit)	Ratio for C_{max} , calculated as follows: $R_{C_{max}} = C_{max\ Period\ 2} / C_{max\ Period\ 1}$
$R_{AUC_{0-inf}}$ (no unit)	Ratio for AUC_{0-inf} , calculated as follows: $R_{AUC_{0-inf}} = AUC_{0-inf\ Period\ 2} / AUC_{0-inf\ Period\ 1}$

Parameters (unit)

Definition

C_{trough} (unit)	Concentration at the end of a dosing interval before the next dose administration
---------------------	---

9.2.2. Plasma pharmacokinetic analysis

Listings with plasma concentrations (including PK blood sampling dates and times) and PK parameters will be provided by treatment group and subject. These listings will be generated for all subjects with an available PK profile (complete or incomplete), including those who are excluded from the PKS.

Plasma concentrations and PK parameters of RO7017773, and Itraconazole and its metabolite (hydroxy-itraconazole) including descriptive statistics will be presented in tables separately for each treatment group.

Individual plasma concentration versus time profiles of RO7017773, and Itraconazole (and metabolite) will be presented graphically on linear and log/linear coordinates for each subject with all treatment groups received by the subject on the same graph.

The graph of arithmetic mean \pm SD over time will be provided for plasma concentration of RO7017773, and Itraconazole (and metabolite) on linear and log/linear coordinates with all treatment groups on the same graph as well as with all analytes on the same graph only for Itraconazole.

The graph of trough concentrations (mean \pm SD) of Itraconazole (and metabolite) on linear coordinates will also be provided.

Scatter plots and box whisker plots will be generated for the comparison of the C_{max} and AUC (AUC_{0-inf} if it can be derived, otherwise truncated as appropriate (AUC_{0-72})) parameters of RO7017773 between the treatment groups.

For the evaluation of the effect of RO7017773 + itraconazole versus RO7017773 alone, the following linear statistical model will be applied to the log-transformed PK variables AUC (AUC_{0-inf} if it can be derived, otherwise truncated as appropriate (AUC_{0-72})) and C_{max} of RO7017773:

$$y_{ij} = \mu + \tau_j + s_i + \varepsilon_{ij} \quad (i = 1, 2, \dots, 12; j = 1, 2)$$

where μ denotes the general mean of the transformed variables, τ_j is the effect of the treatment (RO7017773 + itraconazole versus RO7017773 alone), s_i is the random subject effect and ε_{ij} is the random error (within subject variability). The random subject effect and the random

error are assumed to be independent and normally distributed with zero means and variances σ_s^2 and σ_e^2 respectively.

Least square means with corresponding 90% confidence intervals (90% CIs) will be derived to compare the relative bioavailability of the different treatments.

Under this model the geometric mean ratios (GMRs) $\frac{AUC_{(R07017773 + itraconazole)}}{AUC_{(R07017773 alone)}}$ and $\frac{C_{max(R07017773 + itraconazole)}}{C_{max(R07017773 alone)}}$ are obtained as $\frac{\mu_{\lambda_1}}{\mu_{\lambda_2}} = e^{\lambda_1 - \lambda_2}$, i.e. by exponentiation of the corresponding estimated differences in the analysis of variance (ANOVA) model.

The following SAS code will be used:

```
proc mixed data=ADPP method=REML;
  by PARAMCD;
  class TRTAN USUBJID;
  model ln(AVAL) = TRTAN / solution cl alpha=0.10 ddfm=kr;
  random USUBJID;
  lsmeans TRTAN / cl alpha=0.10;
  estimate 'Test versus Reference' TRTAN -1 1 / cl alpha=0.10 e;
run;
```

10. Pharmacodynamics data

As specified in the section 8.2, the genotyping data will be listed only.

11. Safety data

The safety analyses will be performed on the safety set.

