$R_{C_{max}}$	C_{max} ratio calculated as RO7017773 C_{max} Period 2 over RO7017773 C_{max} Period 1
$R_{AUC_{0-inf}}$	AUC ratios calculated as RO7017773 AUC_{0-inf} Period 2 over RO7017773 AUC_{0-inf} Period 1
RR	RR interval
SAE	Serious Adverse Event
SAP	Statistical Analysis Plan
SAS®	Statistical Analysis System®
SD	Standard Deviation
SEM	Standard Error of the Mean
SOC	System Organ Class
SS	Safety Set
$T_{1/2}$	Apparent terminal elimination half-life
T_{last}	Time to reach last observed plasma concentration
T_{max}	Time to reach maximum observed plasma concentration
TEAE	Treatment-Emergent Adverse Event
WHO	World Health Organisation

1. Introduction

The Statistical Analysis Plan (SAP) details the statistical methodology to be used in analysing study data and outlines the statistical programming specifications, tables, figures and listings. It describes the safety and pharmacokinetics variables and populations, anticipated data transformations and manipulations, and other details of the analyses not provided in the study protocol.

The analyses described are based upon the final clinical study protocol V3.0 dated 14 November 2018 including amendments (#1 and #2) and will be prepared in accordance with the International Conference on Harmonisation (ICH) E9.

The statistical analyses will be performed by the Biostatistics unit of BIOTRIAL BIOMETRICS in agreement with the sponsor.

The SAP will be validated and signed before the study database is locked.

2. Study objectives

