9.1. Generalities

The following rules for **PK parameter calculation** after each administration will be used:

- Actual sampling times will be used for deriving PK parameters.
- If an entire concentration-time profile is below the limit of quantification (BLQ), BLQ values will not be replaced and the profile will be excluded from the PK analysis.
- For plasma concentrations, all BLQ values occurring prior to the first detectable concentration for each administration and negative values will be replaced by "0".
- All BLQ values occurring after the first detectable concentration for each administration and embedded BLQ values (BLQ values between two measurable concentrations) will be treated as missing.
- If a result is BLQ for the pre-dose PK sample, then the result is set to 0, as well as for all other samples being BLQ before the first detectable concentration and occurring before T_{max} . For subsequent time points, the result must be set to missing. Of note, BLQ values that occur between the first detectable concentration and the T_{max} shall be set to missing.
- If the pre-dose concentration is $\leq 5\%$ of the C_{max} value of the corresponding period for a particular subject, that subject's data, without any adjustments, may be included in all pharmacokinetic and statistical analysis. For each period, if the pre-dose value is $> 5\%$ of C_{max} , two analyses will be performed: one with the pre-dose value and the other one with the pre-dose value replaced by 0.

- If there are late positive concentration values following 2 BLQ concentration values in the apparent terminal phase, these values will be evaluated. If these values are considered to be anomalous, they will be set to missing.
- Some conditions for PK parameters have to be fulfilled:
 - 1) the percentage of the extrapolated AUC should not exceed 20% of the AUC_{0-inf} of each individual profile,
 - 2) the elimination rate constant should be determined over a time interval equal to at least $2 \times T_{1/2}$,
 - 3) the determination of λ_z should use only those data points judged to describe the terminal log-linear decline resulting in an adjusted coefficient of determination value $R^2 > 0.7$, and a minimum of 3 data points will be used in calculating λ_z excluding C_{max} .

If these conditions are not fulfilled, the following unreliable PK parameters will not be calculated, will be considered not determined (ND) in the listings and will be excluded from the analysis:

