- 1) if extrapolated AUC $> 20\%$: AUC_{ext} , AUC_{0-inf} and CL/F.
- 2) if the time interval used for the determination of the elimination rate constant is inferior to $2 \times T_{1/2}$ or if the adjusted $R^2 < 0.7$: λ_z , $T_{1/2}$, AUC_{ext} , AUC_{0-inf} , R^2 and CL/F.

The following rules for **plasma concentration versus time graphic representation** will be used:

- No graphic representation will be done if all values are BLQ.
- BLQ values occurring prior to the first detectable concentration will be replaced by “0”.
- All BLQ values occurring after the first detectable concentration will be treated as missing.

The following rules for **mean plasma concentration calculation** will be used:

For BLQ concentrations before the first detectable concentration:

- If more than (or equal to) half of the values are either BLQ values replaceable by zero and/or numeric values: statistics will be calculated with the replaceable and numeric values.
- If more than half of the values are BLQ values not replaceable by zero (i.e., subjects for whom all values are BLQ): only the maximum will be presented and the other statistics will be considered BLQ.

For BLQ concentrations after the first detectable concentration:

- If more than (or equal to) half of the values are not BLQ: statistics will be calculated with BLQ values considered missing data.
- If more than half of the values are BLQ: only the maximum will be presented and the other statistics will be considered BLQ.

For **summary statistics for PK parameters**:

- If more than (or equal to) half of the values are not ND and not missing: statistics will be calculated with the available values.
- If more than half of the values are ND or missing: only the minimum, median and maximum of the available numeric values will be presented. All other statistics will not be calculated and will be presented as ND.

All BLQ concentrations and missing data will be labelled as such in the concentration data listings.

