14.2.1.1.1.2.3	Graphs of plasma concentration means (\pm SD) over time for Itraconazole and metabolite on the same graph - Pharmacokinetic set
14.2.1.1.1.2.4	Graphs of trough concentration means (\pm SD) over time for Itraconazole (and

NUMBER	TITLE
	metabolite) - Pharmacokinetic set
14.2.1.1.2	PK parameters in plasma
14.2.1.1.2.1	RO7017773
14.2.1.1.2.1.1	PK parameters in plasma for RO7017773 - Pharmacokinetic set
14.2.1.1.2.1.2	Scatter plots of C_{max} and AUC (AUC _{0-inf} or AUC ₀₋₇₂) for RO7017773 - Pharmacokinetic set
14.2.1.1.2.1.3	Box whisker plots of C_{max} and AUC (AUC _{0-inf} or AUC ₀₋₇₂) for RO7017773 - Pharmacokinetic set
14.2.1.1.2.1.4	Analysis of drug interaction for C_{max} and AUC (AUC _{0-inf} or AUC ₀₋₇₂) for RO7017773 - Pharmacokinetic set
14.2.1.1.2.2	PK parameters in plasma for Itraconazole (and metabolite) - Pharmacokinetic set
14.2.2	Pharmacodynamics data
14.2.2.1	Graph of individual RO7017773 exposure (C_{max} and AUC _{0-inf} for RO7017773) versus functional status of CYP3A4 and CYP3A5 genotypes after administration on Day 1 in Period 1 - Pharmacokinetic set
14.2.2.2	Graph of individual RO7017773 exposure (C_{max} and AUC _{0-inf} for RO7017773) versus functional status of CYP3A4 and CYP3A5 genotypes after administration on [REDACTED] - Pharmacokinetic set
14.3	Safety data
14.3.1	Adverse events
14.3.1.1	Adverse events - Safety set
14.3.1.2	Treatment-emergent adverse events
14.3.1.2.1	Treatment-emergent adverse events - Safety set
14.3.1.2.2	Treatment-emergent adverse events by intensity - Safety set
14.3.1.2.3	Treatment-emergent adverse events by causality - Safety set
14.3.2	Listing of deaths, other serious and significant adverse events - Safety set
14.3.3	Clinical laboratory data
14.3.3.1	Haematology
14.3.3.1.1	Summary statistics - Safety set
14.3.3.1.2	Listing of subjects presenting abnormal values - Safety set
14.3.3.2	Blood chemistry
14.3.3.2.1	Summary statistics - Safety set
14.3.3.2.2	Listing of subjects presenting abnormal values - Safety set
14.3.3.3	Urinalysis
14.3.3.3.1	Summary statistics - Safety set
14.3.3.3.2	Listing of subjects presenting abnormal values - Safety set
14.3.4	Other safety parameters

NUMBER	TITLE
14.3.4.1	Vital signs data
14.3.4.1.1	Summary statistics - Safety set
14.3.4.1.2	Listing of subjects presenting abnormal values - Safety set
14.3.4.2	Electrocardiogram data - Summary statistics - Safety set
14.3.4.3	Physical examination

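### The SAP defines AUC0-72 as 0 to 24 hours in its parameter table and gives no level, trigger or same-metric rule for switching from AUC0-inf to AUC0-72

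*SAP*

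**What the plan says.** Protocol 9.4.3.1 names AUC and Cmax of RO7017773 as the primary PK variables. AUC is AUC0-inf where derivable, otherwise a truncated AUC with no time given. SAP 9.2.2 supplies the time and models "the log-transformed PK variables AUC (AUC_{0-inf} if it can be derived, otherwise truncated as appropriate (AUC_{0-72})) and C_{max} of RO7017773".

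SAP 9.1 sets the conditions for AUC0-inf. One is that "the percentage of the extrapolated AUC should not exceed 20% of the AUC_{0-inf} of each individual profile". AUC0-inf is also voided "if the time interval used for the determination of the elimination rate constant is inferior to" twice the half-life, or if the adjusted R² is too low. Parameters that fail "will be considered not determined (ND) in the listings and will be excluded from the analysis". SAP 9.1 has a threshold rule, "If more than half of the values are ND or missing: only the minimum, median and maximum" are shown, but it covers summary statistics only.

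In the SAP 9.2.1 parameter table, the AUC0-72 row reads "Area under the plasma concentration-time curve from time zero to 24 hours (only for RO7017773"). The SAP abbreviation list gives 72 hours for the same parameter.

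Three places bear on whether the two metrics can meet in one model:
- The SAS code in SAP 9.2.2 runs separately by parameter code.
- The abbreviation list defines the ratio as "AUC ratios calculated as RO7017773 AUC_{0-inf} Period 2 over RO7017773 AUC_{0-inf} Period 1".
- The output list in SAP 14.2 titles the model table "Analysis of drug interaction for C_{max} and AUC", followed by AUC0-inf or AUC0-72 as alternatives.

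**The concern.** There are two defects in operative text. The first is a plain contradiction about the window of the fallback metric. The wording repeats the AUC0-24 row directly above it, so it looks like a copying slip, but it sits in the table from which the parameter would be programmed.

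The second is a gap between two sections. SAP 9.1 works per profile and removes failures. SAP 9.2.2 offers an alternative metric but does not say whether the choice is made per profile, per participant or for the study, or how many failures prompt it. Two programmers could produce different AUC ratios from the same data and both claim to follow the SAP.

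The losses would not be random. Both the extrapolation rule and the interval rule remove long half-lives, and Protocol 4.3 expects that itraconazole may prolong elimination. Missing values would therefore fall mainly in Period 2, in the participants with the slowest elimination. The random-subject model keeps their Period 1 values but does not undo that selection.

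**Working it through.** The documents state no figure to reproduce here: half-life, the expected ratio and the RO7017773 sampling column are redacted.

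**Inputs.** From the documents: Period 1 PK visits to Day 8, which is 7 × 24 = 168 h after dosing, and Period 2 visits to Day 16 (Protocol 4.1). Assumed: Period 2 RO7017773 dosing on Day 4, inferred from the post-dose safety grid in SAP 11.3.1, and RO7017773 sampling to Day 16 (12 × 24 = 288 h) or only to Day 12 (192 h). Also assumed: Period 1 half-life h of 12, 20 or 30 h, a true AUC0-inf ratio R of 3, and lognormal variability.

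**When a value is voided.** In a one-compartment approximation the extrapolated fraction is 2^(−t/T½). It exceeds 20% when T½ > t/log2(5) = t/2.322.
- 168/2.322 = 72 h (Period 1)
- 288/2.322 = 124 h (Period 2, Day 16)
- 192/2.322 = 83 h (Period 2, Day 12)

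**Effect of dropping voided values, by hand.** Let Period 2 half-life be the product of a lognormal Period 1 half-life (log-variance vT) and a lognormal ratio (vR), kept only if below 124 h. With a = [ln 124 − ln(3h)]/√(vT+vR), the voided share is 1 − Φ(a). The ratio in complete pairs is 3·exp[−(vR/√(vT+vR))·φ(a)/Φ(a)]. For h = 30 h and CVs of 35% for both:
- vT = vR = ln(1.1225) = 0.1156 and √(vT+vR) = 0.481
- a = (4.820 − 4.500)/0.481 = 0.667, so 25% are voided
- φ/Φ = 0.427, and the ratio is 3·exp(−0.240 × 0.427) = 2.71

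Keeping unpaired Period 1 values, as the SAP's mixed model does, lowers this further. In simulations of 14 participants with the SAP 9.1 rules applied and the random-intercept model fitted, it becomes 2.61.

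**Truncated windows.** With the same window t in both periods, the ratio is R(1 − 2^(−t/(hR)))/(1 − 2^(−t/h)). For t = 72 and h = 12: 3 × 0.750/0.984 = 2.29. For t = 24 and h = 12: 3 × 0.370/0.750 = 1.48.

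Estimates when the true ratio is 3 (model rows simulated with constant inhibition; CVs are for half-life/ratio):

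| Analysis | h = 12 h | h = 20 h | h = 30 h |
|---|---|---|---|
| AUC0-inf, voided dropped, 288 h, CVs 35%/35% | 2.99 | 2.87 | 2.61 |
| Period 2 share voided in that row | 0.6% | 7% | 25% |
| Same, CVs 30%/20% | no bias | 2.98 | 2.85 |
| Same, sampling to 192 h, CVs 35%/35% | 2.91 | 2.60 | 2.21 |
| Same, sampling to 192 h, CVs 30%/20% | 2.99 | 2.85 | 2.55 |
| 0 to 72 h in both periods | 2.29 | 1.85 | 1.58 |
| 0 to 24 h in both periods | 1.48 | 1.29 | 1.19 |

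For a true ratio of 2 (288 h, CVs 35%/35%), the estimates are 2.00, 1.99 and 1.92.

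**Inhibition that wears off.** If inhibition ends 48 to 72 h after the last itraconazole dose, the true ratio at h = 30 h is 2.38 to 2.46 and the estimate is 2.38 to 2.47. The bias disappears.

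**The case against.** A reader might infer that the model will combine AUC0-inf and AUC0-72 within participants. The sentence in SAP 9.2.2 permits it, and at h = 30 h (CVs 35%/35%, 288 h) substitution by profile would give 2.15 for a true 3. But the two are separate parameters, the code runs by parameter code, the output titles give them as alternatives, and the ratio takes AUC0-inf in both periods. Combining them is the less likely reading.

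A reader might also infer that the fallback will be computed over 24 hours. The parameter's name and the abbreviation list both say 72, so a programmer would probably notice. The 0 to 24 h row of the table shows why the slip should be corrected, not what is expected to happen.

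The strongest reply concerns size. Itraconazole stops on Day 9, so constant inhibition to Day 16 is doubtful. Protocol 4.4 says dosing maintains itraconazole over the RO7017773 profile and calls the duration of inhibition sufficient. If RO7017773 is given on Day 4, that is about 5 to 6 days, which argues against Period 2 half-lives near 124 h. Protocol 4.3.2 also calls the sampling times adequate for the elimination phase. The study is exploratory, and with an assumed within-subject CV of 30% the 90% confidence limits at n = 12 lie a factor of 1.24 either side of the estimate, wider than most of these shifts. The analysis-set definition in SAP 7.1 may also exclude participants with incomplete data, which would leave complete pairs and less bias.

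All of this stands as a limit on size. None of it supplies the missing rule or removes the contradiction.

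**Conclusion.** The textual point holds with high confidence: the AUC0-72 window is contradicted within the SAP, and the switch has no level, trigger or same-metric requirement. The likely consequence is an AUC0-inf model with some of the longest Period 2 half-lives missing, and a ratio pulled toward 1.

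The documents do not support a claim that the ratio will be materially biased. Under constant inhibition and sampling to 288 h, a true 3 becomes between 3.00 and 2.61. Sampling to 192 h would make it worse, and inhibition that ends soon after the last itraconazole dose removes the bias. Every one of these figures rests on assumed half-lives, variability and sampling, in a mono-exponential model. Severity is minor.

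**What to change.** Before database lock:

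1. Correct the AUC0-72 row in SAP 9.2.1 to zero to 72 hours, to agree with the parameter name and the abbreviation list.
2. State in SAP 9.2.2 that the AUC metric is chosen once for all participants and both periods and that the two are never combined in one model. Give a numeric trigger for moving to AUC0-72. One option is to extend the more-than-half rule of SAP 9.1 from summary statistics to the model.
3. If any AUC0-inf is not determined, add a sensitivity model that keeps the flagged values. Show the extrapolated percentages and warn that values voided for a short elimination interval or poor fit are unreliable. Report it beside AUC0-72 in both periods for all participants.
4. Label any AUC0-72 ratio as a truncated-window estimate that understates the AUC0-inf ratio when elimination is prolonged.

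The cost is one table row, a few sentences and one or two extra model runs. The downside is that some poorly extrapolated values appear in a caveated table. No visit or sample changes.

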11.1. Adverse events

Adverse events, including pre-treatment serious events only, will be recorded from the time of consent through 15 to 20 days after the end of treatment period.

Adverse events will be coded according to MedDRA Version 21.1.

A treatment-emergent adverse event (TEAE) is an adverse event that occurs on or after the first IMP administration of each period or that was present prior to dosing but was exacerbated on or after the first IMP administration of each period.

Adverse events will be summarised in tables as follows [overall and by System Organ Class (SOC) and Preferred Term (PT)]:

- Number and percentage of subjects with at least one adverse event and number of occurrences of an adverse event by treatment group (before any treatment and after first intake of each treatment) and overall,
- Number and percentage of subjects with at least one TEAE and number of occurrences of a TEAE by treatment group,

- By intensity, with the number and percentage of subjects with at least one TEAE and number of occurrences of a TEAE by treatment group,
- By causality (to RO7017773 alone, to itraconazole alone and to both RO7017773 and itraconazole), with the number and percentage of subjects with at least one TEAE and number of occurrences of a TEAE by treatment group.

If there are only a few adverse events (≤ 10), only a listing will be generated.

All adverse events reported in the electronic Case Report Form (eCRF) will be listed with the SOC, the PT and the investigator's verbatim. All TEAEs will also be listed with the SOC and the PT. An additional listing will be provided for AEs leading to death and other serious and significant AEs (SAEs or AEs leading to study withdrawal).

Note:

- i. In the descriptive tables, the number of subjects with at least one adverse event/TEAE for a given PT will also correspond to the number of adverse events/TEAEs whatever the number of occurrences during the studied period.
- ii. In case of a change of intensity or causality for an event during the same treatment period, the intensity will be the highest recorded intensity and the causality will be the highest likelihood recorded.
- iii. A treatment-emergent AE will be associated with the treatment group of the current period if this AE starts between the first IMP administration of the current period and the first IMP administration of the next period.

